#### ***D4B Sending the Push Reports***

The push reports will be sent to surgeons at sites who have signed the Exhibit B-1 over the course of four weeks. This will include all surgeons at sites who have signed Exhibit B-1s before the initiation of the push report launch for whom the study team has contact information. Sites who did not sign the Exhibit B-1 and/or surgeons for whom the team was unable to gather updated email addresses for push reporting and/or for whom the email address was no longer valid will be excluded from the intervention arm and moved to the control arm.

The push report will be sent via using a secure email client. The email will be sent to the email the surgeon has provided to MSQC as their official email. In the case of multiple email addresses, the study team will send the email to the most secure account available (e.g. .edu, .gov, .org rather than Yahoo, Gmail, etc).

All surgeons who practice at hospitals and for whom we have a current email address who have signed the Exhibit B-1 will receive a push report email from the study team. Read receipts will be embedded in each push report email to see if surgeons have opened the push report. If they have not, the study team will follow-up with the same email on a weekly basis for a total of 4 weeks or until they open the email, whichever comes first. Emails will be sent to prescribers in this fashion unless they directly contact the study team to request otherwise and/or their hospital/health system revokes permission.

[figure not shown]

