## D4C Push Report Data Collection

We will collect prescribing data reported through the existing MSQC mechanism for five months from the date of the first push report. In addition to the standard variables reported to MSQC, the study team will collect data on surgeon interaction with the email push report. We will collect information such as who opens the email, who logs into the MSQC platform after receiving the email, and who directly contacts the study team and why. This information will be used to inform who needs to continue receiving push reports, be used in research analyses, and inform quality improvement opportunities based on this methodology.

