## D5 Feedback Surveys

Following receipt of the push report(s), the study team will send up to two surveys to all prescribers who received the push report to collect information about usability and acceptability of the email push reports. Surgeons who open the push report will be sent a survey invitation the following day and another two weeks later. The first survey will ask about their reactions to the push report and ask surgeons for permission to be contacted again regarding a qualitative interview whereas the second will ask about any actions taken after receiving the push report. Surgeons who do not open any of the push reports will be sent a different survey invitation. These surgeons will be asked a single question regarding what could be improved. Each invitation will contain a link to the appropriate survey programmed in University of Michigan secure Qualtrics and will be preceded by the approved consent form.

Figure 2: Push Report Feedback Timeline

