## D7 Qualitative Interview

In addition to receiving up to two surveys, surgeons who indicate in the first survey that they are interested in scheduling or learning more about scheduling a qualitative interview will be emailed by the study team with the appropriate information. The purpose of this fifteen minute interview is to examine the preferences and experiences of surgeons who have received this feedback. The study

team will reach out to the surgeon individually and work with them to schedule a time to conduct the interview.

The interview will take place via Zoom or on the phone at the mutually agreeable time. A trained member of the study team will obtain consent from the participant prior to the interview. The participant must consent to having audio from the interview recorded in order to participate and language indicating this will be included in the consent. The interview will be recorded on an encrypted recorder or directly in the Zoom platform and then saved directly to an encrypted study drive. Once the audio recording is obtained and saved a study team member or third party who have an agreement with the University of Michigan will transcribe the interview. The transcription will also be saved to an encrypted study drive with the participant's study ID.

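### For survey and interview routing, the read receipt is the only stated evidence of opening, so a reader whose receipt never registers drops out of the acceptability and adoption data

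*Protocol*

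**What the plan says.** D4B of the Protocol sets the detector: "Read receipts will be embedded in each push report email to see if surgeons have opened the push report". Where no opening is seen, "the study team will follow-up with the same email on a weekly basis for a total of 4 weeks or until they open the email". The mailing also ends if the surgeon asks for that or the hospital withdraws permission.

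D4C collects wider interaction data: "who opens the email, who logs into the MSQC platform after receiving the email, and who directly contacts the study team and why". On its use, D4C says: "This information will be used to inform who needs to continue receiving push reports, be used in research analyses".

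D5 opens with a general statement that "the study team will send up to two surveys to all prescribers who received the push report", and then splits them. Surgeons who open the report are invited the next day to a survey on reactions, which also asks permission for interview contact, and two weeks later to a survey on actions taken. For the rest, "Surgeons who do not open any of the push reports will be sent a different survey invitation", and it holds one question about improvements. D7 offers the interview to "surgeons who indicate in the first survey that they are interested in scheduling or learning more about scheduling a qualitative interview".

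Section B makes acceptability and adoption part of the stated aim, to be assessed by survey and interview. E2 lists the survey and interview items as exploratory.

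**The concern.** The routing rule acts while data are being collected. A surgeon sent the wrong questionnaire never gives the missing answers, and no later analysis can recover them.

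The surgeons at risk are those who read the report, and perhaps acted on it, but for whom no receipt registers. They are labelled non-openers, their reactions and actions go unasked, and the interview is closed to them. Their one answer is filed with those of surgeons who never saw the report.

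The protocol holds other evidence that could flag such a surgeon, namely "who logs into the MSQC platform after receiving the email, and who directly contacts the study team and why", but D5 does not use it for routing. What is at stake is the recorded opening rate and the acceptability and adoption findings.

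**Working it through.** The documents give no opening rate and no receipt error rate, so there is no figure of the plan to reproduce. The check has two parts.

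**Tracing one surgeon through the text.** Take a surgeon who reads the report without a receipt registering.
- D4B: no receipt, so the same email goes out weekly for up to four weeks.
- D5: the non-opener survey goes only to surgeons who opened none of the mailings, so one missed receipt is not enough. Every mailing the surgeon opened must have been missed.
- If all were missed, the surgeon gets the one-question survey and neither opener survey.
- D7: without the first opener survey there is no stated route to interview.
- No section reclassifies a surgeon who shows no receipt but contacted the study team about the report.

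**Illustration on assumed values.** Let t be the true proportion opening and s the proportion of openings that a receipt captures. Assume t = 0.6 and s = 0.5, 0.7 or 0.9. Take four mailings.

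If misses are persistent (the same surgeon is missed every week):
- true openers never detected = 1 - s
- recorded opening = t × s
- share of labelled non-openers who had opened = t(1 - s)/(1 - ts)

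If misses are independent and all four mailings are opened:
- true openers never detected = (1 - s)^4
- share of labelled non-openers who had opened = t(1 - s)^4 / [(1 - t) + t(1 - s)^4]

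| | s = 0.5 | s = 0.7 | s = 0.9 |
|---|---|---|---|
| Persistent: never detected | 50% | 30% | 10% |
| Persistent: recorded opening | 30% | 42% | 54% |
| Persistent: share of non-openers | 0.30/0.70 = 43% | 0.18/0.58 = 31% | 0.06/0.46 = 13% |
| Independent: never detected | 6.25% | 0.81% | 0.01% |
| Independent: share of non-openers | 0.0375/0.4375 = 8.6% | 0.00486/0.40486 = 1.2% | 0.00006/0.40006 = 0.015% |

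Letting t run from 0.4 to 0.8 widens the persistent share to 6% (t = 0.4, s = 0.9: 0.04/0.64) through 67% (t = 0.8, s = 0.5: 0.40/0.60).

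**Bias in an opinion item.** Let d be the difference in the favourable proportion between detected and missed openers. Under persistent misses, the error for all true openers is (1 - s) × d. It is zero if d = 0. If d is 20 points it is 10, 6 or 2 points at s = 0.5, 0.7 or 0.9.

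**The case against.** Several stronger readings are tempting, and the documents do not support them.

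- *The receipt alone decides who is re-mailed.* It does not. D4C gives log-ins and contacts a role in deciding who keeps receiving reports, and D4B stops on request. What remains is that D4B's own stopping rule mentions opening, request and revocation but not log-in, so the two sections do not match.
- *The opening rate is understated.* D4B says only that receipts are embedded. The technology and its direction of error are not given, and false openings are also possible.
- *The implementation results are biased.* That needs misses that persist across mailings and different views among the missed surgeons. Neither is shown. Independent misses make the problem small, although a surgeon who has read the first email has little reason to open identical repeats, which weakens the protection from repeated mailing.
- *Any later MSQC log-in should count as opening.* Sections C2 and D4A describe a platform that already exists and gives surgeons regular reports. A log-in may be routine and says little about the email.

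It is also fair to say that missed readers still get one question, that the results concerned are exploratory, and that the survey instruments and the timeline figure are not available here, so a screening item in them cannot be excluded. These points limit the concern's weight. They do not supply a fallback in the written rule.

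**Conclusion.** The point holds for survey and interview routing. There the receipt is the only stated evidence of opening, and a reader missed on every mailing is lost to the reaction, action and interview data. This can distort the exploratory acceptability, adoption and opening-rate results, on two conditions: the misses persist, and the missed surgeons differ from those detected.

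The 13-43% figure for mislabelled non-openers rests on an assumed 60% true opening rate and the persistent-miss extreme. It is an illustration, not an estimate, and neither size nor direction can be fixed from the documents.

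The primary prescribing outcome comes from MSQC data (E1), and arm membership depends on site sign-off and a usable email address (D4B). Neither depends on receipts. This is a cheap improvement, not a threat to the main comparison.

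**What to change.** 1. In D5, start the non-opener survey with one question: *Did you see the prescribing report?* Branch a yes to the opener items, including actions taken and permission for interview contact. This catches missed receipts whatever their cause or rate. It does not correct false openings.
2. Treat direct contact with the study team about the report as evidence of exposure. Do not count an MSQC log-in by itself as opening.
3. Report opening by source of evidence: receipt, self-report, contact and log-in, shown separately.
4. Reconcile D4B with D4C so that both state the same evidence for ending the weekly mailing.

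The cost is one branching question in the existing Qualtrics survey, a short wording change in the protocol and a slightly longer non-opener survey.

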## D4C Push Report Data Collection

We will collect prescribing data reported through the existing MSQC mechanism for five months from the date of the first push report. In addition to the standard variables reported to MSQC, the study team will collect data on surgeon interaction with the email push report. We will collect information such as who opens the email, who logs into the MSQC platform after receiving the email, and who directly contacts the study team and why. This information will be used to inform who needs to continue receiving push reports, be used in research analyses, and inform quality improvement opportunities based on this methodology.

## D5 Feedback Surveys

Following receipt of the push report(s), the study team will send up to two surveys to all prescribers who received the push report to collect information about usability and acceptability of the email push reports. Surgeons who open the push report will be sent a survey invitation the following day and another two weeks later. The first survey will ask about their reactions to the push report and ask surgeons for permission to be contacted again regarding a qualitative interview whereas the second will ask about any actions taken after receiving the push report. Surgeons who do not open any of the push reports will be sent a different survey invitation. These surgeons will be asked a single question regarding what could be improved. Each invitation will contain a link to the appropriate survey programmed in University of Michigan secure Qualtrics and will be preceded by the approved consent form.

Figure 2: Push Report Feedback Timeline

## D7 Qualitative Interview

In addition to receiving up to two surveys, surgeons who indicate in the first survey that they are interested in scheduling or learning more about scheduling a qualitative interview will be emailed by the study team with the appropriate information. The purpose of this fifteen minute interview is to examine the preferences and experiences of surgeons who have received this feedback. The study

team will reach out to the surgeon individually and work with them to schedule a time to conduct the interview.

The interview will take place via Zoom or on the phone at the mutually agreeable time. A trained member of the study team will obtain consent from the participant prior to the interview. The participant must consent to having audio from the interview recorded in order to participate and language indicating this will be included in the consent. The interview will be recorded on an encrypted recorder or directly in the Zoom platform and then saved directly to an encrypted study drive. Once the audio recording is obtained and saved a study team member or third party who have an agreement with the University of Michigan will transcribe the interview. The transcription will also be saved to an encrypted study drive with the participant's study ID.

## **E. Statistical Design**

### ***E1 Primary Outcome***

The primary outcome will be the average opioid prescribed (measured in oral morphine equivalents [OMEs] adjusted for the surgery type following the intervention. Only cases with valid prescribing data and surgeon NPI will be included for analysis. Prescribing data will be collected for five months following the first push report.

### ***E2 Exploratory Outcomes***

Exploratory outcomes will be the rate of prescribing within the MSQC guidelines over the same year following the intervention. We will also evaluate the survey and interview items collected on acceptability, ease of use, relevance, utility, and appearance.

